8.1 Data Analysis

All eligible subjects will be assigned a unique identification number upon enrollment in the study. Initial study data will be recorded on a printed form, which will be later converted to an IRB approved electronic database, REDCap. Only study personnel will have access to this database. All potential identifiers will be kept separately in a safe location at the PI's office in NYU Skirball 9th floor, where it will be placed under double lock and key and the PI will have access. After verification of entered data at completion of the study all potential identifiers will be stripped from the database.

Descriptive statistics, including frequency tables, measures of center and variability, and graphical displays will present baseline subject characteristics. Similar analyses will present values of platelet activity measures.

Primary Platelet Activity Measures: LTA and MPA To test the hypothesis that platelet activity measurements are independently associated with 30-day (Aim 1) and long-term (Aim 2) cardiovascular events in patients undergoing lower extremity revascularization we will employ the following analysis. For Aim 1, platelet activity will be measured preoperatively and the main outcome will be 30-day cardiovascular events. For Aim 2, platelet activity will be measured 48 hours postoperatively and the main outcome will be long-term (mean follow-up ~ 2 years) cardiovascular events. We will perform univariate analysis to investigate the association between LTA and MPA platelet activity measures and cardiovascular events. Next, we will examine differences in sociodemographic/clinical factors between participants with and without a cardiovascular event using two-sided tests of proportions for categorical variables (chi-square, Fisher's exact) and t-tests or non-parametric alternatives (e.g., Wilcoxon test) for continuous measures.

The analysis plan outlined above for the primary platelet activity measures will be applied to the set of secondary measures including thrombin. In addition, the analysis plan outlined above for the primary outcome measures will be applied to the secondary outcome measures including major bleeding.

To identify novel mRNA-miRNA target pairs involved in platelet activation, we will computationally inversely correlate miRNA expression with expression of gene targets using established prediction databases

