We designed the PACE clinical study initially to investigate platelet activity in PAD patients and the incidence of major adverse cardiac and limb events after lower extremity revascularization. PACE was set up to investigate the relationship between platelet activity and cardiovascular risk. Many studies suggest the overlapping nature of cardiovascular risk and dementia. Thus, we would like to extend findings that have established the link between heart disease and dementia to platelet activity and dementia. The comprehensive platelet characterization already performed would facilitate our study investigating the association between platelets and cognitive decline in this cohort of patients with established CVD. We will attempt to call all living participants and obtain telephone consent for the additional measure, assess vital status, and perform a validated survey of subclinical cognitive impairment in the PACE cohort with 2 previously validated neuropsychiatric tests that are frequently used in aging studies: TICS and Montreal Cognitive Assessment, MoCA. Both tests can be easily done remotely by trained personnel and are particularly good at detecting early subclinical impairment.

3. Specific Aims

Aim 1. To determine whether preoperative platelet activity measurements are independently associated with short-term cardiovascular events in PAD patients undergoing non-emergent lower extremity revascularization. We will characterize the platelet phenotype in 350 PAD patients before vascular surgery and use Cox proportional hazard models to determine the independent association of the platelet phenotype with risk of cardiovascular events in the first 30 days after surgery.

Aim 2. To determine whether postoperative platelet activity measurements are independently associated with long-term cardiovascular events in patients with established PAD. We will characterize the postoperative platelet phenotype following surgery and use Cox proportional hazards models to determine the independent association of the platelet phenotype with risk of long-term composite of myocardial infarction, stroke, or all-cause mortality with a mean follow-up of 2-years following vascular surgery.

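### Section 8.1 sets out only unadjusted analyses for an independent-association hypothesis and omits the Aims' Cox models; the Wilcoxon power stated as 80% is about 73% on its own inputs

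*Combined protocol and SAP*

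**What the plan says.** Section 3 (Specific Aims) names the model for each main aim. For Aim 1 the plan is to "use Cox proportional hazard models to determine the independent association of the platelet phenotype with risk of cardiovascular events in the first 30 days". For Aim 2 it is to "use Cox proportional hazards models to determine the independent association of the platelet phenotype with risk of long-term composite of myocardial infarction, stroke"; the composite also counts death from any cause, and the follow-up is given as "with a mean follow-up of 2-years following vascular surgery".

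Section 8.1 states the same objective, "To test the hypothesis that platelet activity measurements are independently associated with 30-day (Aim 1) and long-term (Aim 2) cardiovascular events", and introduces the analysis that is to serve it. The first step reads: "We will perform univariate analysis to investigate the association between LTA and MPA platelet activity measures and cardiovascular events". The second reads: "Next, we will examine differences in sociodemographic/clinical factors between participants with and without a cardiovascular event using two-sided tests", with chi-square, Fisher, t or Wilcoxon tests. The paragraph ends there, with a complete sentence. The plan is then reused twice: "The analysis plan outlined above for the primary platelet activity measures will be applied to the set of secondary measures including thrombin", and "the analysis plan outlined above for the primary outcome measures will be applied to the secondary outcome measures including major bleeding".

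Section 8 (Statistical Analysis) bases power on a two-sided Wilcoxon test at the 0.025 level with 200 participants, an expected 30-day event rate of 22% and a difference of 0.5 SD, and states 80%. LTA and MPA are co-primary, so 0.025 is 0.05/2. Planned enrolment elsewhere in the protocol is 350. In the text available, the power sentence breaks off before its end; this is treated as lost text and not as a fault in the plan.

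**The concern.** A univariate association cannot show that a marker is independent of age, sex, medication or comorbidity. Section 8.1 promises that conclusion and then lists no step that could deliver it. The comparisons of clinical factors by event status feed no stated model, and no part of the document lists adjustment covariates for Aims 1 and 2 or a rule for choosing them.

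As the text stands, three places point to three analyses: Cox models in the Aims, univariate analysis in 8.1, and an unadjusted Wilcoxon test behind the sample size. The choice between an adjusted and an unadjusted result, and the choice of covariates, could therefore be made after the data are seen. If the event/no-event comparisons were used to pick covariates, the selection would be data-driven. The reuse clauses carry the same gap into the secondary measures and into major bleeding.

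The stated power is not the power of the analysis that the Aims promise, so it was worth checking both that figure and the power of an adjusted model.

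**Working it through.** **Inputs from the documents.** Event rate 22%; difference 0.5 SD; two-sided 0.025 (critical value 2.241); N = 200 (section 8) and N = 350 (planned enrolment). Events: 0.22 × 200 = 44, leaving 156 without an event; 0.22 × 350 = 77, leaving 273.

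**1. The plan's own figure.** For normal data the Wilcoxon test has efficiency 3/π relative to the t-test, so power ≈ Φ(0.5 × √[(3/π) × n1 × n0 / N] − critical value).

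- N = 200: 44 × 156 / 200 = 34.32. The first term is 0.5 × √(0.955 × 34.32) = 2.862. Φ(2.862 − 2.241) = 0.733. Simulation (20,000 runs): 0.722.
- N = 350: 77 × 273 / 350 = 60.06. The first term is 3.787. Φ(3.787 − 2.241) = 0.939. Simulation: 0.936.
- N = 200 at two-sided 0.05: Φ(2.862 − 1.960) = 0.817. Simulation: 0.810.

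The stated 80% is therefore not reproduced at 0.025; about 233 participants would be needed. It fits 0.05. Equal group sizes do not explain it either: 100 against 100 at 0.025 gives about 89%.

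**2. Power of an adjusted Cox model for Aim 1.** The documents give no hazard ratio and no covariates, so two assumptions are needed. First, the adjusted association is as large as the planned crude one. A difference of 0.5 within-group SD (the basis on which the Wilcoxon formula works) at 22% events corresponds to a log hazard ratio of 0.445 per SD of the marker, solved numerically for a normally distributed marker. Second, the covariates explain a share R² of the marker's variance, taken as 0 to 0.3. Power ≈ Φ(0.445 × √[events × (1 − R²)] − 2.241).

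| R² | N = 200 (44 events) | N = 350 (77 events) |
|---|---|---|
| 0 | 0.761 | 0.952 |
| 0.1 | 0.712 | 0.928 |
| 0.2 | 0.655 | 0.895 |
| 0.3 | 0.590 | 0.847 |

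Simulated Cox models with four terms (2,000 runs) agree at the two ends: 0.763 and 0.605 at N = 200, 0.954 and 0.843 at N = 350.

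**3. Room for covariates.** Marker plus three covariates is four terms. Aim 1 gives 44/4 = 11 events per term at N = 200 and 77/4 ≈ 19 at N = 350. No long-term event rate is stated for Aim 2. At ten events per term, four terms need 40 events, that is a rate of 40/200 = 20% or 40/350 = 11.4%.

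**The case against.** The strongest reply is that 8.1 names its hypotheses as Aim 1 and Aim 2, and the Aims already assign a Cox model to each. A univariate step followed by a look at clinical factors is an ordinary prelude to such a model, and no sentence in 8.1 excludes adjustment. This stands in part. A reader might infer that the study plans no adjusted analysis, or that 8.1 overrides the Aims; the documents support neither. What remains is that the section meant to specify the analysis leaves out the model, and that covariates are specified nowhere.

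A reader might also infer that adjustment is what takes power below 80% at N = 200. It is not. The unadjusted Wilcoxon test is already at about 73%, and a Cox model with R² = 0 is slightly higher, at about 76%.

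Nor do the documents support a claim that the unadjusted test would produce many false positives here. Any such figure depends on drug use, imbalance and drug effects that the documents do not give.

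Finally, the power sentence is cut off, and the missing words might have dealt with adjustment or with 350 participants. That limits what can be said about the full statement. It does not alter the visible figure, whose inputs all precede the break, and the paragraph in 8.1 is complete.

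**Conclusion.** The point holds as an omission and an inconsistency. Section 8.1 states an independent-association hypothesis, lists only unadjusted analyses for it, extends them to secondary measures and outcomes, and does not carry over the Cox models named in the Aims. Separately, the visible power figure is wrong on its own inputs: about 73% and not 80% at N = 200.

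The consequence for power is limited at the planned enrolment. With 350 participants the unadjusted test has about 94% power, and an adjusted Cox model about 95% to 85% over R² of 0 to 0.3. With 200 the adjusted range is about 76% to 59%. The unadjusted figures assume normal data (for LTA, after transformation); the adjusted ones also rest on the assumed R² range and on an adjusted effect as large as the planned crude one. The larger issue is interpretation: without a prespecified model, a claim of independence would depend on choices left open until the data are in hand.

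**What to change.** In section 8.1:

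- Name the Cox model from the Aims as the primary analysis for each co-primary marker, at two-sided 0.025.
- Fix a short covariate set in advance from data already collected, for example age, sex and antiplatelet use at the relevant blood draw. Appendix A schedules medication use at both draws, but whether it identifies antiplatelet drugs must be checked on the case report form, which is not in the text.
- Label the univariate and event/no-event comparisons descriptive, and state that they will not be used to select covariates.
- Apply the same adjusted approach to secondary measures and outcomes, with fewer terms where events are few.
- Use a person-level robust variance, because the inclusion criteria (section 4.g) allow a participant to re-enrol after a later procedure.

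In section 8, restate the Wilcoxon power as unadjusted, about 73% at N = 200 and 94% at N = 350. If adjusted Cox power is added, give it on the same within-group SD basis with the assumed R² range: about 76% to 59% and 95% to 85%.

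The cost is wording and one model per marker. The downside is some loss of precision if the marker correlates with the covariates, modest at N = 350 and larger at N = 200.

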Following the interview and signed informed consent, subjects will have their blood drawn, and will be asked to provide a urine sample prior to surgery. Blood will be obtained from the patient using standard aseptic phlebotomy techniques. Blood will be collected from an arterial line placed for surgery (if available) or at the time of the intravenous line being placed for surgery or using a standard technique of blood drawing. A brief description of the standard technique follows: after cleansing of the venipuncture site with an alcohol wipe and removal of excess alcohol with sterile gauze, a tourniquet will be applied to the patient's bicep region. A 19G or 21G butterfly needle will be inserted into the antecubital vein, the tourniquet will be removed, and free-flowing blood will be collected with minimal trauma and stasis. The needle will be removed when blood collection is complete and sufficient pressure will be applied using sterile gauze at the puncture site until cessation of bleeding. A sterile band-aid will be applied to cover the venipuncture site. For each patient, no more than 60 ml (≈4 table spoons) of blood will be collected in gold (serum separator tube) top, lavender (EDTA anticoagulant) top, green (heparin), blue (sodium citrate anticoagulant) top and Pax gene tubes. Approximately 40 cc of blood will be used for the different measurements of platelet function, inflammation, coagulation and other biomarkers of cardiovascular risk and approximately 20 cc of blood will be used to purify platelet RNA, whole blood RNA and DNA and then stored in -80C for the RNA, microRNA, and DNA profiling. The samples will be placed in the PI's lab at NYU New Science Building- Cardiology 7th floor without any identifying information other than a code number. The code number will not be based on any information that could be used to identify the subject (for example, social security number, initials, birth date, etc). The master list linking names to code numbers will be kept in a locked file cabinet, separate from all research information in the PI's office at NYU Skirball 9th floor and will be accessed by the PI. The urine specimen will be collected to measure abnormalities in thrombosis, hemostasis and inflammation as well. At the end of the patient recruitment and measurement of platelet function (probably within 4 years time), based on ones level of platelet activity, thrombin generation, coagulation and inflammation we will measure RNA, microRNA, and DNA in patients with different phenotypes of vascular disease, markers of thrombosis/hemostasis, and events from the stored specimens.

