Blood samples will be assigned a unique code number and stored in the PI's lab without any identifying information other than a code number. The unique code number will not be based on any information that could be used to identify the subject (for example, social security number, initials, birth date, etc.). The master list linking names to code numbers will be kept in a locked file cabinet, separate from all research information placed under double lock and key at the PI's office at NYU Skirball 9th floor. All confidential data will be stored with a unique code as an identifier and will be protected by a double electronic lock. All physical data will be kept under double physical lock. Access to the data will be given to the study personnel only.

Samples will be stored for no more than 10 years following completions of the study. Samples will be used for testing other potential biomarkers in patient plasma and/or serum related to other endpoints not specified in the protocol (e.g. cancer, metabolic disease, etc.). Genetic testing will not be conducted on stored samples. Results of the future research will not be shared with the subjects or their study doctor, and will not become part of the medical records.

Subjects can request for withdrawal of samples at any time by contacting PI [name] in writing. His mailing address is [name]. Withdrawing

Authorization only affects uses and sharing of information after written request has been received, and subject may not withdraw his/her Authorization for uses or disclosures that have previously been made or must continue to complete analyses or report data from the research.

f. After Surgery and Follow Up

Starting on the day of surgery and continuing throughout hospitalization, a physician monitors the patient's course for clinically evident cardiovascular events (MI, stroke, TIA, major bleeding, kidney disease, or any surgical complication). Blood collections and/or ECG's that are performed as part of routine care and/or for study purposes will be recorded and may be used to help ascertain whether a cardiovascular and/or bleeding event has occurred. After hospital discharge, patients will be contacted by telephone (or during their routine clinical follow-up) at 30 days and every 6-month thereafter out to 5-years. At the patients' follow-ups they will be asked questions about their health, lifestyle, and medication use.

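### Section 8.1 applies event-versus-no-event tests of clinical factors to the long-term outcome as well, although follow-up is unequal and the tests ignore time at risk

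*Combined protocol and SAP*

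**What the plan says.** Section 8.1 introduces a single plan for "30-day (Aim 1) and long-term (Aim 2) cardiovascular events in patients undergoing lower extremity revascularization we will employ the following analysis". For Aim 2 it states that "the main outcome will be long-term (mean follow-up ~ 2 years) cardiovascular events". After an unspecified univariate analysis of LTA and MPA, it will examine "differences in sociodemographic/clinical factors between participants with and without a cardiovascular event using two-sided tests of proportions for categorical variables" and use "t-tests or non-parametric alternatives (e.g., Wilcoxon test) for continuous measures". Nothing restricts these comparisons to 30 days, and section 8 mentions no censoring, person-time or fixed horizon. Section 8.1 then adds that "the analysis plan outlined above for the primary outcome measures will be applied to the secondary outcome measures including major bleeding".

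Section 4.f schedules contacts "at 30 days and every 6-month thereafter out to 5-years". Section 4.c expects recruitment and platelet measurement to be complete in about four years.

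Section 3 (Specific Aims) names Cox proportional hazards models for the association of the platelet phenotype with events in both Aim 1 and Aim 2. The Aim 2 composite there is myocardial infarction, stroke or all-cause mortality.

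**The concern.** At 30 days nearly everyone has the same window, so comparing those with and without an event is reasonable. For Aim 2, a participant event-free after a few months of observation is classed with one event-free after five years. A characteristic related to length of follow-up (through enrolment period or ease of tracing, for example) will then differ between the two groups even if it has no effect on risk, and a real association can be masked. For long-term bleeding, a yes/no comparison would also place a participant who dies early without bleeding among those free of bleeding, unless the analysis says otherwise.

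At stake are the p-values for sociodemographic and clinical factors on the long-term and secondary outcomes.

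**Working it through.** The plan gives no figure for this point. Its only power statement (section 8) concerns the 30-day outcome and is not needed here.

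**Inputs from the documents.** N = 350 (sections 3 and 4.a); mean follow-up about 2 years (sections 3 and 8.1); contacts to 5 years (4.f); recruitment over about 4 years (4.c).

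**Assumptions not in the documents.** A constant hazard h of 0.08 to 0.16 per year; uniform entry over 4 years with one closing date at year 4, so follow-up F is uniform on 0 to 4 years with mean 2; a binary factor with no effect and 50% overall prevalence, whose prevalence changes linearly by s from the start to the end of enrolment; tests at two-sided 5%.

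**Step 1: why time at risk matters.** The chance of being in the event group is 1 − exp(−hF). At h = 0.12 it is 1 − exp(−0.06) = 5.8% after 6 months and 1 − exp(−0.60) = 45% after 5 years, at identical risk.

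**Step 2: link between factor and follow-up.** Var(F) = 16/12. The difference in mean follow-up between factor levels is (s/4)(16/12)/0.25 = 4s/3. Hence:
- s = 0.2 (40% to 60%): 0.27 years
- s = 0.4 (30% to 70%): 0.53 years
- s = 0.8 (10% to 90%): 1.07 years
- maximum, s = 1: 1.33 years

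**Step 3: false difference in event shares.** Overall share P = 1 − (1 − e^(−4h))/(4h). Difference between levels D = 2s{E[e^(−hF)] − ½E[F e^(−hF)]}, where E[F e^(−hF)] = [1 − e^(−4h)(1 + 4h)]/(4h²).

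For h = 0.12, s = 0.4: E[e^(−hF)] = 0.3812/0.48 = 0.794, so P = 0.206. E[F e^(−hF)] = 0.0842/0.0576 = 1.462. D = 0.8 × (0.7942 − 0.7309) = 0.051, so event shares are about 18.1% and 23.1% with no true effect.

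**Step 4: rejection rate of chi-square.** Standard error = √[P(1 − P) × 4/350] = √(0.206 × 0.794 × 0.01143) = 0.0432. D/SE = 1.17, and Φ(1.17 − 1.96) + Φ(−1.17 − 1.96) = 0.22.

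**Step 5: range.** The approximation in steps 3 and 4 beside the simulated rates, for h = 0.08 to 0.16:

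| Difference in mean follow-up | Chi-square, approximation | Chi-square, simulated | Log-rank, simulated |
|---|---|---|---|
| 0 | 5% | about 5% | 4-6% |
| 0.27 years | 8-10% | 8-10% | 4-6% |
| 0.53 years | 16-27% | 16-26% | 4-6% |
| 1.07 years | 49-76% | 52-76% | 4-6% |

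The two agree to within a few percentage points. A separate simulation with different inputs (hazards 0.10 to 0.20, uniform follow-up within each level) gave 18-29% at a 0.5-year difference and 53-78% at 1 year, with log-rank at 4.4-5.2%.

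**The case against.** The strongest reply is that the main long-term analysis is already time-to-event: section 3 states Cox models for the platelet phenotype. That stands. A reader of section 8.1 alone might infer that the Aim 2 platelet result rests on chi-square or Wilcoxon tests, or that the markers lose power that way. The documents do not support this. The two-group tests attach to sociodemographic and clinical factors, and the only Wilcoxon test named for a platelet marker is in the power statement, for short-term events. What remains is that section 8.1 does not repeat the Cox commitment and leaves its univariate marker analysis open.

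A reader might also infer that these comparisons decide which factors go with events or which enter the adjusted models. Section 8.1 says only that differences will be examined; it ties no selection rule or threshold to them.

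Finally, the error needs a link between factor and follow-up length, and the documents report none. With no link, chi-square keeps its level. Rates above one half need a factor whose prevalence moves from about 10% to 90% over enrolment. This limits the size of the problem but does not remove it, because the tests give no protection if a link exists.

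The short end of the follow-up range is inferred from the schedule. No long-term bleeding endpoint or horizon is defined, so the handling of early deaths is a gap in the plan, not a stated rule. For the Aim 2 composite, death is itself an event and does not compete.

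**Conclusion.** The point holds for the long-term comparisons of sociodemographic and clinical factors, and for any long-term secondary outcome to which the same plan is applied. As written, those p-values are unreliable for any factor related to length of follow-up. The excess error runs from none (no link) through 8-10% and 16-26% to 52-76% for a very strong link, against 4-6% for log-rank. All of these rest on the assumed hazards, enrolment pattern and closing date. The 30-day comparisons are sound in this respect, and the Aim 2 platelet association is not affected if the section 3 models are used. Severity is minor to moderate; it does not reach the level of a must-fix.

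**What to change.** In section 8.1:
- Limit the chi-square, Fisher's exact, t and Wilcoxon comparisons of participants with and without an event to the 30-day outcome.
- For Aim 2 and any long-term secondary outcome, use univariable Cox models or log-rank tests with censoring at last contact. Say that the univariate analysis of LTA and MPA for Aim 2 is also a Cox model, in line with section 3.
- For long-term major bleeding, censor at death for the cause-specific hazard ratio, and show cumulative incidence with death as a competing event.

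The cost is one paragraph of wording and slightly more analysis work. The Cox models already planned need the same event and last-contact dates.
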